#### **Section 1: Administrative information**

#### **Trial status**

VITaCCA was approved by the ethics committee at Amsterdam UMC, location VUmc (Protocol Record METC-2018.120) and registered at ClinicalTrials.gov (NCT03509662) on April 26, 2018 https://clinicaltrials.gov/ct2/show/NCT03509662 and at European Clinical Trials Database (EudraCT) (2017-004318-25) on June 8, 2018. https://www.clinicaltrialsregister.eu/ctr-search/trial/2017-004318-25/NL

Enrollment of patients in the VITaCCA trial started at October 7, 2019 and finished at February 11, 2024. Last patient 180-day follow-up was at August 29, 2024.

#### Trial protocol and statistical analysis plan (SAP)

The study protocol has been published in *Trials* [1]. A detailed pre-specified statistical analysis plan (SAP) of the VITaCCA-trial is presented in this document (v1.0). The SAP has been written by [name], [name], [name] and [name], the trial statistician/independent methodologist.

#### **Section 2: Introduction**

#### **Background** and rationale

The prognosis of patients suffering from cardiac arrest is still poor, with high morbidity and mortality. Once the circulation has recovered, reactive oxygen species (ROS) generated during the ischemia/reperfusion response further contribute to organ damage and death. Intravenous vitamin C may improve the clinical outcome of post-cardiac arrest patients as vitamin C directly scavenges free radicals, repairs oxidized scavengers and reduces the production of ROS. The 'Early high-dose vitamin C in post-cardiac arrest syndrome (VITaCCA) trial' will evaluate whether an early high-dose intravenous vitamin C improves organ function in patients after cardiac arrest [1].

#### **Objectives**

The primary objective of the trial is to determine whether early high-dose intravenous vitamin C can improve organ function in patients after cardiac arrest, and to explore the optimal dosing regimen for high dose intravenous vitamin C.

#### **Section 3: Trial methods**

## Trial design

The VITaCCA trial is a double-blind, multicenter, randomized placebo-controlled trial with a three-arm comparative design. Patients are randomized to one of 3 treatment groups. Group 1 will be treated with placebo (0.9% NaCl), group 2 with a twice-daily intravenous bolus of 1.5g vitamin C and group 3 with a twice-daily intravenous bolus of 5g vitamin C for 4 days or until ICU discharge. In addition, all patients receive intravenous thiamine 200 mg every 12h for 4 days or until ICU discharge.

The clinical trial has been conducted in six Dutch ICUs: Amsterdam UMC, location VUmc (coordinating center), Erasmus MC, Amphia Hospital, OLVG, location East, Maasstad Hospital and Gelderse Vallei Hospital.

#### Randomization

Eligible patients will be randomized using a computer-generated randomization list in a 1:1:1 ratio to one of the three treatment groups. Randomization will be stratified by site and age ( $\leq$ 66 and  $\geq$ 66 years) in blocks of 6. Patients were randomized only if early administration of the first dose ( $\leq$ 5 hours after ROSC) was still feasible. Deferred informed consent was obtained  $\leq$ 72 hours after inclusion/randomization.

#### Sample size

Eighty-two patients per group are needed to detect a treatment effect of 2 SOFA points with 90% power and a two-sided alpha of 0.01 [1]. The study aimed to include 3x 90 patients to compensate for 10% loss after randomization for late outcomes.

#### Framework

A superiority framework will be used for primary and secondary outcomes.

#### **Interim analysis**

A blinded interim analysis focused on mortality will be caried out by the trial statistician after inclusion of 135 evaluable patients. Analysis will be group comparative. The data safety monitoring board (DSMB) will be blinded but may be unblinded by the trial statistician. The DSMB can advise to stop further recruitment in case of significantly higher mortality in the

vitamin C group(s) compared to placebo and after thorough examination of the clinical content.

## Timing of final analysis

The final analysis for the primary and secondary endpoints is planned when the 180-day follow-up is completed for the last patient included.

The full dataset will be assessed for correctness and completeness of the data by reviewing all individual records in Castor. Any errors, discrepant or missing data will be queried and resolved. Thereafter, the database will be locked and exported for statistical analyses. First, the analyses will be performed with blinded data, i.e. included patients will be assigned to intervention A, B or C. Conclusions about the primary outcome will be drawn according to the blinded results and reported in short (abstract) format. This blinded abstract will be included as supplementary material in the paper in which the main results will be presented.

#### Timing of outcome assessments

Detailed information about timing of the outcome assessments can be found in the methods section of the trial protocol paper [1].

When patients were discharged early, i.e. during the first 4 days of ICU-admission, data was also collected on the day of discharge except for diuresis and fluid balance as these do not reflect a full 24 h period of time. Data was not collected on the ward after ICU-discharge.

# **Section 4: Statistical principles**

#### **Confidence intervals**

Effect estimates will be reported with confidence intervals. The confidence intervals will be 95% and two-sided.

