#### 'Modified intention-to-treat analysis' (mITT) – Primary analysis

- All randomized and treated patients
  - Without patients who received the first dose with a delay (>5 hours after ROSC).
  - Without patients who turned out not to be eligible (not fulfilling all inclusion criteria).
- For this analysis the trial is powered: 270 patients, 90 in each arm.

For clarification: treated patients who met the inclusion criteria but suddenly fulfilled one of the 3 upper safety exclusion criteria were also included in the primary mITT analysis, but further administration of study medication was terminated.

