# **Section 6: Analysis**

#### **Primary outcome and analyses**

The primary outcome is the delta 96 h resuscitation-sequential organ failure assessment score (ΔR-SOFA96-baseline): The R-SOFA score at 96 h after randomization minus the score after ROSC (baseline R-SOFA score). Our primary outcome has been described in detail in our published protocol [1]. All relevant data for the primary outcome was collected for all included patients according to the protocol. When included patients were transferred to another ICU prior to T96 h, data was retrieved from the involved hospitals (with consent).

The difference in  $\Delta R$ -SOFA96-baseline score between intervention and control groups will be analyzed using linear mixed model analyses, with a random intercept on site level. The analysis will be adjusted for the baseline SOFA-score. When the residuals are not normally distributed the outcome will be transformed before analysis.

Analysis will be performed crude and adjusting for *age* (stratification variable). This age adjusted analysis will be the primary analysis.

In additional analyses, the model will be adjusted for relevant covariates such as delay (time of no flow), total duration of CPR (time of low flow) and first measured pH [2]. Moreover, vitamin C groups will be combined and compared to placebo as well to estimate the overall effect of vitamin C.

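### The trial is sized at a two-sided 0.01 level, but the SAP never says that this level decides the primary result and prescribes only 95% intervals

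*SAP*

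**What the plan says.** - SAP Section 3, Sample size: the target is 82 per group for a difference of 2 points, calculated "with 90% power and a two-sided alpha of 0.01". This is the only significance level in the document. The recruitment target is 90 per arm.
- SAP Section 4, Confidence intervals: "The confidence intervals will be 95% and two-sided". The rule covers all effect estimates, and the primary outcome is not treated separately.
- SAP Section 4, definition of the mITT population: "For this analysis the trial is powered: 270 patients, 90 in each arm". No level is named.
- SAP Section 6, Primary outcome and analyses: "This age adjusted analysis will be the primary analysis". No test level is given, and the contrasts are described only as intervention against control groups. Pooling is listed among the additional analyses: "Moreover, vitamin C groups will be combined and compared to placebo as well to estimate the overall effect of vitamin C".
- SAP Section 3, Timing of final analysis: "Conclusions about the primary outcome will be drawn according to the blinded results". No threshold is attached.
- SAP Section 3, Trial design: a "randomized placebo-controlled trial with a three-arm comparative design".

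**The concern.** The level that decides the primary outcome is core content of an analysis plan. Here it appears only as an input to the sample size. The inferential output that the plan does prescribe, a 95% interval, corresponds to a 0.05 test per contrast, and no multiplicity rule accompanies it. Whoever writes the blinded conclusion will have a 95% interval in hand and no instruction on whether excluding zero is enough.

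At stake is the type I error rate for which the trial was sized. A contrast with p between 0.01 and 0.05 excludes zero by its 95% interval and fails at the design level. Coding the arms A, B and C makes it harder to choose a level that favours a known arm, but it does not fix the level.

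**Working it through.** **Inputs from the SAP.** Difference 2 points, power 90%, two-sided level 0.01, 82 per group, 90 per arm recruited, three equal arms (Sample size; Randomization; mITT definition).

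**Assumptions.** The SAP gives no SD, so it is back-solved below and then varied. Two dose-versus-placebo contrasts are inferred from the three arms and from pooling being only an additional analysis. All figures are unadjusted two-sample normal approximations.

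**1. The plan's own figure.** Without an SD, 82 cannot be reproduced independently. Solving n = 2(z₀.₉₉₅ + z₀.₉₀)² SD² / Δ² for the SD:

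82 = 2 × (2.576 + 1.282)² × SD² / 2², so SD ≈ 3.32 (3.29 with a t-test).

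The planned figure is therefore consistent with its stated inputs if the SD is about 3.3.

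**2. What the 0.01 level cost.** For the same effect and power, the ratio of sample sizes does not depend on the SD:

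(1.960 + 1.282)² / (2.576 + 1.282)² = 0.706, and 82 × 0.706 = 57.9, so 58 per group.

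That is 24 fewer per group, or 72 fewer over three groups.

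**3. Family-wise error, two contrasts sharing placebo.** With equal arms the two statistics have correlation 0.5, and the error is 1 − P(|Z₁| < c, |Z₂| < c).

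| Level per contrast | c | Two contrasts | Bound if independent |
|---|---|---|---|
| 0.05 | 1.960 | 9.1% | 1 − 0.95² = 9.75% |
| 0.01 | 2.576 | 1.9% | 1 − 0.99² = 1.99% |

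Adding the pooled contrast gives about 9.6% and 2.1%.

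**4. Where the two readings disagree.** With SD 3.32 and 90 per arm:

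- SE = 3.32 × √(2/90) = 0.495.
- The 95% interval excludes zero from 1.960 × 0.495 = 0.97 points.
- The 0.01 test rejects from 2.576 × 0.495 = 1.27 points.

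Observed differences of about 0.97 to 1.27 points are positive on one reading and negative on the other.

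**5. Chance that a given contrast has p between 0.01 and 0.05, at 90 per arm.** Apart from a negligible opposite tail, this is Φ(2.576 − δ/SE) − Φ(1.960 − δ/SE), where δ is the true difference.

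| Assumed SD | δ = 2 points | δ = 1 point |
|---|---|---|
| 3.0 | 2.3% | 24.2% |
| 3.32 | 5.3% | 23.5% |
| 4.0 | 13.7% | 20.4% |
| 5.0 | 22.2% | 16.0% |

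The maximum over all effects is 24.2%, at δ/SE = 2.27, which is 1.12 points when the SD is 3.32.

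**6. Power if 0.01 is applied.** With SD 3.32, power for 2 points is 90.0% at 82 per arm and 92.9% at 90 per arm. Holding to 0.01 loses nothing that was planned.

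**The case against.** The strongest reply is that the SAP states exactly one alpha, 0.01, and that the mITT section ties the primary analysis to the power calculation. On this view the primary test runs at the only level stated, the 95% intervals are a reporting convention, and no text makes 0.05 the deciding level. The published protocol, cited for the sample size and not available for this check, may also state the test level.

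Much of this is fair. The 95% rule does not contradict or withdraw the 0.01, and testing at 0.01 is the more natural reading. But it remains an inference. The SAP has a section on statistical principles, puts only the 95% rule there as a level, and does not refer to the protocol for a decision threshold.

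A second reply concerns size. The error rates hold only if conclusions are read from the 95% intervals, the contrasts are inferred, and the SD is back-solved. The calculations ignore the baseline and age adjustment and the site intercept. Scoring deaths before 96 hours as 24 points (Planned sensitivity analyses) makes any simple normal SD doubtful. The 1-point scenario lies close to the worst case. These limits stand, so the discordance figures are illustrations. The saving at 0.05 is also measured against an uncorrected test. Against a Bonferroni 0.025 per contrast the ratio is (2.241 + 1.282)² / (2.576 + 1.282)² = 0.834, or about 69 per group, a saving of 13 rather than 24. That reduces the contrast but does not make the 58 wrong. The SAP does not say why 0.01 was chosen, so it should not be described as a multiplicity correction.

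**Conclusion.** The concern holds, as an omission rather than a contradiction: no statement in the SAP makes 0.01 the level that decides the primary outcome. It should be fixed because it can change the headline conclusion, although it does not invalidate the design.

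The family-wise figures assume two contrasts, equal arms and a normal approximation, but no SD. The width of the disputed band and the chance of landing in it depend on the assumed SD. At the 2-point design effect that chance runs from 2.3% to 22.2% for SDs of 3.0 to 5.0, and is 5.3% at the back-solved SD. If 0.01 governs both contrasts, family-wise error is well under 5% and no further multiplicity rule is needed.

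**What to change.** In SAP Section 4, with a cross-reference from the primary analysis in Section 6 and from the blinded conclusion in Section 3:

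1. State that each dose-versus-placebo contrast in the age-adjusted mITT analysis is tested at two-sided 0.01.
2. Give 99% intervals for these contrasts, or keep 95% intervals and label them descriptive.
3. State that the pooled contrast, already listed as additional, carries no confirmatory claim.
4. If another level is intended, state it with its multiplicity rule and the reason for departing from the sample size paragraph.

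This should be settled before the blinded conclusion is written. The SAP does not say whether that has happened. If it has, the clarification should be dated and reported as made afterwards.

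The cost is one or two sentences. Intervals at 99% are about 31% wider (2.576 / 1.960 = 1.314), while labelling the 95% intervals descriptive costs nothing. Planned power is unchanged because it was computed at 0.01.

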## Adherence and protocol deviations

Information regarding adherence to the study intervention is collected in Castor for each patient, most importantly 'first dose <5 hours after ROSC' and 'total doses of study medication administered'. All protocol deviations will be noted on a protocol deviation form and shared with the coordinating center. Analysis will be performed according to the intention-to-treat principle, see later.

The study procedures were terminated when a patient did not fulfill all inclusion criteria and/or when a patient suddenly fulfilled one of the 3 upper safety exclusion criteria (see section 5 for study criteria), when more information became available after the study had already been started (after at least one dose of study medication). Deferred consent was asked in all cases in order to follow-up every randomized and treated patient.

#### **Definition of analysis population**

The patient populations for the final analyses are defined as follows, with approval of the Data Safety Management Board and the ethics committee:

#### 'Modified intention-to-treat analysis' (mITT) – Primary analysis

- All randomized and treated patients
  - Without patients who received the first dose with a delay (>5 hours after ROSC).
  - Without patients who turned out not to be eligible (not fulfilling all inclusion criteria).
- For this analysis the trial is powered: 270 patients, 90 in each arm.

For clarification: treated patients who met the inclusion criteria but suddenly fulfilled one of the 3 upper safety exclusion criteria were also included in the primary mITT analysis, but further administration of study medication was terminated.

## 'Full analysis set' (ITT)

- All patients who met the in- and exclusion criteria, for whom an early administration
  of the first dose (<5 hours after ROSC) was still feasible, were randomized and treated
  according to the protocol.

  - o Including treated patients, who turned out not to meet all inclusion criteria.
  - Including treated patients, who suddenly fulfilled one of the 3 upper safety exclusion criteria.
- This analysis will contain >270 patients.

As can be understood from the information above, all randomized patients who received at least one dose ('treated') will be analyzed in the ITT-analysis, despite not fulfilling the inclusion criteria or fulfilling the exclusion criteria. These patients have not been subsequently excluded. As described earlier, further study treatment was terminated, but the patients were followed up according to the protocol.

Patients for whom deferred consent was not obtained <72 hours were excluded from the study and all analyses, except patients who died before consent could be obtained (<72 hours).

# **Section 5: Trial population**

## Screening data and eligibility

The inclusion and exclusion criteria [1] are presented below:

Table 1. Inclusion and exclusion criteria	
Inclusion criteria	Exclusion criteria
An out-of-hospital cardiac arrest with return of	Terminal renal insufficiency, i.e. receiving renal
spontaneous circulation (ROSC);	replacement therapy (RRT);
Ventricular fibrillation (VF) or ventricular tachycardia	Known glucose 6-phosphate dehydrogenase deficiency
(VT) as first registered cardiac rhythm a ;	(risk of hemolysis);
Glasgow Coma Scale (GCS) ≤8 b .	History of urolithiasis, oxalate nephropathy or
	hemochromatosis;
	Treatment limitations c .
a If an automated external defibrillator advised to shock, then VF or VT was registered by the device.	
b The last GCS-score before the start of sedatives will be used.	
c The presence of treatment limitations will only be assessed at the moment of randomization.	

## The following screening data is collected:

- Number of OHCA patients screened
- Number of OHCA patients eligible for inclusion
- Number of eligible OHCA patients included in the VITaCCA-trial
- Reasons for non-eligibility
- Reasons for not including eligible patients

#### A flow diagram of all randomized patients is constructed, including:

- Number of randomized patients in whom the study was eventually not initiated, with reason
- Number of randomized patients in whom study treatment A, B or C was initiated
- Number of excluded patients, with reason
- Number of patients in each arm included in the ITT-analysis
- Number of patients in each arm included in the mITT-analysis
- Number of patients (in ITT- and mITT-analysis) in whom study treatment was discontinued, with reason

#### Follow-up

There are two main reasons for lost to follow up:

- Included patients who are transferred to an ICU or ward of another hospital. Primary endpoint data (to calculate SOFA T96 h) will be collected from the hospitals involved (with consent). Other secondary endpoints will be missing, except for the questionnaires at day 28 and day 180.
- Included patients or their relatives who are not reachable by phone for questionnaires at day 28 and day 180.

The amount and timing of patients lost to follow up will be mentioned in the manuscript or supplementary file.

## **Description of baseline characteristics**

Patients will be described with respect to age, gender, body mass index, medical history of hypertension, diabetes, myocardial infarction, heart failure, COPD and stroke, Charlson Comorbidity Index (CCI), whether the arrest was witnessed, whether bystander-CPR was performed, AED-usage, amount of shocks administered, first monitored rhythm, time from cardiac arrest to initiation of CPR, time from cardiac arrest to sustained ROSC (>20 minutes), time from ROSC to first dose of study medication, and clinical characteristics on admission (first measured pH, first lactate level, ST-segment elevation myocardial infarction, Glasgow Coma Scale).

Categorial variables will be presented as numbers with percentages. Continuous variables will be presented as mean with standard deviation or as median with interquartile range when appropriate. Q-Q plots will be assessed visually to check if a given variable follows a normal distribution.

# **Section 6: Analysis**

#### **Primary outcome and analyses**

The primary outcome is the delta 96 h resuscitation-sequential organ failure assessment score (ΔR-SOFA96-baseline): The R-SOFA score at 96 h after randomization minus the score after ROSC (baseline R-SOFA score). Our primary outcome has been described in detail in our published protocol [1]. All relevant data for the primary outcome was collected for all included patients according to the protocol. When included patients were transferred to another ICU prior to T96 h, data was retrieved from the involved hospitals (with consent).

The difference in  $\Delta R$ -SOFA96-baseline score between intervention and control groups will be analyzed using linear mixed model analyses, with a random intercept on site level. The analysis will be adjusted for the baseline SOFA-score. When the residuals are not normally distributed the outcome will be transformed before analysis.

Analysis will be performed crude and adjusting for *age* (stratification variable). This age adjusted analysis will be the primary analysis.

In additional analyses, the model will be adjusted for relevant covariates such as delay (time of no flow), total duration of CPR (time of low flow) and first measured pH [2]. Moreover, vitamin C groups will be combined and compared to placebo as well to estimate the overall effect of vitamin C.

## Secondary outcomes and analyses

The secondary outcomes are summarized in a SPIRIT figure [1].

Dichotomous secondary outcomes include:

- Delirium
  - o CAM-ICU score, ICDSC-score or DOSS-score (yes or no)
- ICU-acquired weakness
  - o Medical Research Council sum score (yes: <48, no: 48-60)
- Need for renal replacement therapy (yes or no)
- At day-28 and day-180:
  - o Survival (yes or no)

Dichotomous variables will be presented as numbers with percentages. For dichotomous variables logistic regression analyses will be carried out. Results will be presented with odds ratios and 95% confidence intervals.

Ordinal secondary outcomes include:

- Renal
  - o Calcium oxalate crystals in urine (negative, few or many)
- At day-28 and day-180:
  - o Functional outcome (mRS scale 0-6)
  - o Neurological outcome (CPC scale 0-5)

Ordinal variables will be presented as numbers with percentages. For ordinal variables a multinomial logistic regression analysis will be carried out. Results will be presented with odds ratios and 95% confidence intervals.

Continuous secondary outcomes include:

- Organ failure:
  - o SOFA-score
- Neurological:
  - o Glasgow Coma Scale
  - Neuron-specific enolase (NSE) ng/mL
  - o The Health Utilities Index-3
- Cardiac/hemodynamics:
  - $\circ$  Troponin ng/L
  - $\circ$  CK U/L
  - $\circ$  CK-MB  $\mu$ g/L
  - Vasopressor duration hours
  - Vasopressor-free days
- Lung:
  - Lung injury score
  - Ventilation duration days
  - Ventilator-free days
- Renal
  - Creatinine clearance μmol/L
  - Oxalic acid (urine) mmol/24h

- Inflammation
  - C-reactive protein mg/L
- Oxidative stress
  - Oxidation-reduction potential (ORP) mV
  - o Antioxidant capacity (AOC)  $\mu$ C
- Pharmacokinetics
  - O Plasma vitamin C concentration μmol/L
- Other clinical outcomes
  - o ICU-stay days
  - Hospital stay days

Continuous variables will be presented as mean with standard deviation or as median with interquartile range when appropriate. Q-Q plots will be assessed visually to check if a given variable follows a normal distribution. For continuous variables linear regression analyses or linear mixed model analyses will be carried out when appropriate. Results will be presented with effect sizes estimates and 95% confidence intervals. When the residuals are not normality distributed the outcome will be transformed before analysis. Analyses will be adjusted for baseline values if applicable.

Secondary analyses will be performed crude. In an additional analysis, vitamin C groups will be combined and compared to placebo as well to estimate the overall effect of vitamin C.

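### mRS and CPC are classed as ordinal but given a multinomial model that ignores the ordering, with no reference outcome category, overall test or single directional estimate for either scale

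*SAP*

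**What the plan says.** Under Secondary outcomes and analyses (Section 6), the list that opens "Ordinal secondary outcomes include" has three entries: "Calcium oxalate crystals in urine (negative, few or many)", "Functional outcome (mRS scale 0-6)" and "Neurological outcome (CPC scale 0-5)". The last two are assessed at day 28 and day 180. For all three the SAP states: "For ordinal variables a multinomial logistic regression analysis will be carried out". Results are to be given as odds ratios with 95% intervals. For description, "Ordinal variables will be presented as numbers with percentages".

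The same section makes the secondary analyses crude and adds: "In an additional analysis, vitamin C groups will be combined and compared to placebo as well". No different model is named for that comparison. The Framework paragraph in Section 3 applies superiority to the secondary outcomes.

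On the order of work, Timing of final analysis says: "First, the analyses will be performed with blinded data, i.e. included patients will be assigned to intervention A, B or C".

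Nowhere does the SAP state a reference outcome category, a joint test across categories, a cumulative-odds model, a common odds ratio or a split into good and poor outcome for mRS or CPC.

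**The concern.** Multinomial logistic regression, as named, treats the outcome levels as unordered. Applied to a seven-level scale, it returns six separate odds ratios per comparison, each setting one level against a reference level. None of them answers the question that a superiority framework poses for such a scale: did patients end up better or worse overall? The reference arm is evidently placebo. The reference outcome level is left open, and so is the way in which six or five odds ratios are to be read together.

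What is at stake is a clear, pre-specified answer for two patient-centred secondary outcomes, and possibly some efficiency. The primary conclusion is not at stake.

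**Working it through.** **Step 1. Count the planned estimates (inputs all from the SAP).** A multinomial model gives (levels − 1) odds ratios per comparison.

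- mRS: 7 levels, so 6 per vitamin C arm. CPC: 6 levels as written, so 5 per arm.
- Two arms against placebo, two time points: (6 + 5) × 2 × 2 = 44.
- Combined vitamin C group: (6 + 5) × 2 = 22 more, total 66.
- A proportional-odds model gives one per comparison: 2 outcomes × 2 arms × 2 time points = 8, plus 2 × 2 = 4 for the combined group, total 12.
- Crystals: 3 levels, so 2 odds ratios per arm at each assessment instead of 1. The mismatch is the same but matters little.

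**Step 2. What the open reference category changes.** Assume a placebo mRS distribution (levels 0 to 6, level 6 taken as death) of 12/14/12/8/5/3/46%, and multiply each cumulative odds by 2.0. For level 0, 0.12/0.88 = 0.136 becomes 0.273, a proportion of 21.4%. For death, the cumulative odds 0.54/0.46 = 1.174 become 2.348, leaving 29.9% dead. The odds ratio for level 0 against death is (21.4/29.9)/(12/46) = 2.75. The full sets are:

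| Reference | Expected odds ratios |
|---|---|
| Death | 2.75, 2.18, 1.77, 1.53, 1.40, 1.32 (levels 0 to 5) |
| mRS 0 | 0.79, 0.64, 0.56, 0.51, 0.48, 0.36 (levels 1 to 6) |

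The two sets come from one fit. The 0.36 is 1/2.75, and its interval excludes 1 in 62% of simulated trials under either choice. The choice changes only which weaker contrasts are displayed. With death as reference, the second contrast excludes 1 in 42% of trials. With mRS 0 as reference, none of the other five does so in more than 14%.

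**Step 3. Efficiency, without an outcome distribution.** Suppose a 1-df ordinal test has 80% power at two-sided 0.05, so its noncentrality is (1.96 + 0.84)² ≈ 7.85. Spread over more degrees of freedom, the same noncentrality gives about 56% on 5 df (CPC) and 52% on 6 df (mRS). Recovering 80% would need about 1.63 and 1.74 times the sample. This assumes that odds are proportional.

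**Step 4. Efficiency by simulation (illustration only).** The SAP gives 90 per arm for the mITT population but no mRS distribution, so the distributions are assumed. Each scenario used 40,000 trials, two-sided 0.05 and complete data. The ordinal test is the tie-corrected rank test. The multinomial test is the 6-df likelihood-ratio test, which the SAP does not plan and whose size is 6-7% under no effect.

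| Scenario | Overall multinomial | Survival model | Ordinal |
|---|---|---|---|
| Base distribution, odds ratio 2.0 | 47% | 62% | 73% |
| Base and three other assumed distributions (placebo deaths 32-55%), odds ratio 2.0 | 45-49% | 51-62% | 71-74% |
| Same four, odds ratio 1.75 | 30-33% | 37-45% | 53-56% |
| Deaths 46% to 32%, all extra survivors at mRS 4-5 | 58% | 49% | 15% |

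In the last row the vitamin C distribution is 12/14/12/8/12/10/32%. Its cut-point odds ratios are 1.00 at the first four cuts, then (0.58/0.42)/(0.51/0.49) = 1.33 and (0.68/0.32)/(0.54/0.46) = 1.81. Reporting them would expose the pattern that the single summary hides.

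**The case against.** The strongest reply is that the multinomial model is valid and avoids the proportional-odds assumption, and that calling a scale ordinal does not oblige anyone to fit a cumulative model. That stands as far as validity goes. The SAP, however, does not give this as its reason, and it plans no overall test, which is what would make the unordered model informative.

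A second reply is that little is withheld. With treatment arm as the only predictor the model is saturated, so a table of counts by arm contains every contrast, and a reader could derive a common odds ratio from it. This also largely stands, provided the table is shown by arm. A result that readers must derive for themselves is still not a pre-specified one.

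Third, the wording may be loose and ordinal regression intended. If so, the repair is one term.

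Several stronger readings are tempting but not supported:

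- A reader might infer that the SAP has no directional estimate of neurological outcome at all. It lists the Health Utilities Index-3 as a continuous outcome with an effect estimate and interval. The gap concerns mRS and CPC.
- A reader might infer that the choice of reference category could reverse or manufacture a finding. It re-parameterises the same crude fit, and the strongest contrast appeared under both choices tested.
- A reader might treat the many intervals as an inflated error rate. The SAP states no rule by which any single interval excluding 1 counts as success, so no such rate belongs to the plan.
- A reader might infer that the ordinal model is always more powerful. The last scenario shows the reverse, and the SAP has no data to say which pattern applies.
- A reader might suspect a reference category chosen to favour vitamin C. The analyses are first run with coded arms. This protects only in part, since category counts are visible by then, but nothing in the document points to such a choice.

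**Conclusion.** The point holds as a mismatch between outcome class and model, together with an incompletely defined analysis. It is not an invalid test. Its firm size is the count: 44 odds ratios for mRS and CPC (66 with the combined group), where an ordinal model gives 8 (12), and no single directional estimate for either scale. The primary analysis and survival are untouched, and survival carries part of the same signal. The power figures rest on assumed distributions, complete data and, for the 73% against 47%, proportional odds. They indicate what may be lost and do not estimate this trial's power. The change should be made, because it is cheap and settles how two important secondary outcomes will be read.

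**What to change.** Replace the sentence on ordinal variables with the following commitments:

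1. Proportional-odds (cumulative-logit) regression is the main analysis of the ordinal outcomes. It gives one common odds ratio with 95% CI for each vitamin C arm against placebo and one for the combined group.
2. The direction of each scale is stated, including the level that codes death. The SAP gives only the ranges. Crystals keep the order negative, few, many.
3. The odds ratio at each cut-point is always reported beside the common odds ratio. The planned counts and percentages per category are shown by arm.
4. The main model will not be switched on the basis of the data.
5. If multinomial regression is kept, it is a sensitivity analysis. Its reference category and one overall test are stated before the coded A/B/C analysis starts.

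The cost is a few sentences and no new data. The downside is that a common odds ratio can mask opposing shifts, such as more survivors with severe disability, and has little power against them. The cut-point odds ratios, the category table and the separate survival model would show such a pattern.
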